3.4 Study Endpoints

3.4.1 Primary Endpoint

The primary endpoint of this study is safety and tolerability of SBC-103 in subjects with MPS IIIB. The safety assessments will include the following:

- Incidence of AEs, SAEs, and IARs;
- Changes from baseline in clinical laboratory tests (hematology, serum chemistry, and urinalysis) and CSF findings (cell counts, glucose, and protein);
- Changes from baseline in 12-lead electrocardiograms (ECGs);
- Changes in vital signs during and post-infusion, relative to pre-infusion values;
- Physical examination findings;
- Use of concomitant medications/therapies;
- Assessment of ADAs, including seroconversion rate, time to seroconversion, and ADA titer by time point, peak ADA titer, and ADA titer status (positive/negative), and the effect of ADAs on the safety of SBC-103, including the relationship between ADA-positive subjects and the incidence of IARs.

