Due to the limitations on the volume of blood collection that is considered to be acceptable in young children with very small total circulating blood volumes; see Committee for Medicinal Products for Human Use (CHMP) and Pediatric Committee (PDCO) guidance (EMEA/536810/2008, adopted 25 June 2009), the blood laboratory tests will be ranked by tier. Per individual, the study-related blood loss should not exceed 3% of the total blood volume during a period of four weeks and should not exceed 1% at any single time. The total volume of blood is estimated at 80 to 90 mL/kg body weight; 3% corresponds to about 2.4 to 2.7 mL blood per kg body weight.

Only Tier 1 assessments (see Table 4) are considered mandatory and all efforts should be made to collect these samples in all subjects. Samples for the Tier 2 or Tier 3 assessments will be collected if permitted based on the blood or CSF volume threshold for a subject's weight, as well as the subject's clinical status.

All tests will be performed by a central laboratory with the exception of the urine pregnancy test (or serum pregnancy test if the urine cannot be collected), CSF routine findings, and (as of 23 March 2015) all coagulation panels, which will be done locally.

Clinical laboratory samples will be stored by the Sponsor or designee in a secure and controlled environment until analysis, and will be destroyed by the Sponsor or designee after all worldwide obligations have been met, or sooner if required by local regulations.

Refer to the laboratory manual for further details regarding the collection, processing, and storage of clinical laboratory samples.

Page 67 of 121

Lab Panel	Tier	Matrix	Tests		
Hematology	1	Whole Blood	White blood cell count; red blood cell count; hemoglobin; hematocrit; MCV, MCH, MCHC; platelet count; neutrophil; lymphocytes; monocytes; eosinophils; basophils;		
Serum Chemistry	1	Serum	ALT, AST, alkaline phosphatase, GGT, albumin, total bilirubin, serum electrolytes (sodium, potassium, chloride, calcium, magnesium, phosphorus), glucose, creatinine, bicarbonate, total protein, BUN		
Coagulation	1	Plasma ^c	PT, INR ^c		
Urinalysis	N/A	Urine	pH, clarity, color, specific gravity, glucose, ketones, blood, protein, nitrite, and leukocytes (microscopic examination will only be done if urinalysis is positive for blood, nitrite, or leukocytes, or if protein is $>1+$)		
Pregnancy test ^a	N/A	Urine			
MPS IIIB	1	Dried blood spot	NAGLU enzyme activity		

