Diagnostics	1	Dried blood spot	NAGLU gene mutation analysis		
РК	1	Serum	PK profile		
РК	3	CSF	SBC-103 concentration		
ADA	1	Serum	Anti-SBC-103 Antibody (IgM, IgG and IgE). Subjects who experience a moderate or severe IAR should have a serum sample collected for ADA during the next study visit (\geq 4 days after the IAR) prior to the infusion.		
Biomarkers	1	Serum	HS (total and NRE)		
	2	Serum	Ferritin and chitotriosidase		
	2	Plasma	Glutamic acid and glycine		
	2	Serum	IgG, inflammatory markers, and exploratory biomarkers		
	N/A	Urine	HS (total and NRE)		
	1	CSF	HS (total and NRE)		
	2	CSF	HGF, calbindin D, Tau, pTau, amyloid β , albumin, IgG, glutamic acid and glycine		
	1	CSF/Serum ^b	CSF/Serum Albumin Index (CSF-AI) and IgG index ([CSF/serum IgG ratio] / [CSF-AI])		
	2	CSF ^c	Routine findings (cell counts, glucose, protein) ^c		
DNA Sample ^d	2	Whole blood			
Serum Tryptase	If clinically indicated	Serum	Subjects who experience a moderate or severe IAR should have a serum sample collected for analysis of tryptase 1-3 hours after the IAR onset and another serum sample for tryptase and ADA during the next study visit (\geq 4 days after the IAR) prior to the infusion.		

Table 4:	Clinical Laboratory Tests
----------	----------------------------------

Key: ADA = anti-drug antibodies; ALT = alanine aminotransferase; AST = aspartate aminotransferase; BUN = blood urea nitrogen; CSF = cerebrospinal fluid; DNA = deoxyribonucleic acid; GGT = gamma-glutamyl transpeptidase; HGF = hepatocyte growth factor; HS = heparan sulfate; IAR = infusion-associated reaction; IgE = immunoglobulin E; IgG = immunoglobulin G; IgG index = immunoglobulin G index; IgM = immunoglobulin M; INR= international normalized ratio; MCH = mean corpuscular hemoglobin; MCHC = mean corpuscular hemoglobin concentration; MCV = mean corpuscular volume; N/A = not applicable; NRE = non-reducing end; NAGLU = alpha-N-acetylglucosaminidase; PK = pharmacokinetics; PT = prothrombin time.

Unless specified in the SOA, the laboratory tests apply to Part A (Initial Therapy), Part B (Therapy at 1 and/or 3 mg/kg), and Part C (Therapy at 5 and/or 10 mg/kg).

^a Test performed by a local laboratory for all female subjects of child-bearing potential. If a urine sample is not able to be provided, a serum pregnancy test will be performed by a local laboratory.

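### Table 4 makes CSF-AI and the IgG index mandatory, but leaves their CSF albumin, CSF IgG and serum IgG inputs, and the CSF findings of the primary safety endpoint, conditional on volume and clinical status

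*Protocol*

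**What the plan says.** **The tier rule (Protocol Section 5.2.1).** "Only Tier 1 assessments (see Table 4) are considered mandatory and all efforts should be made to collect these samples in all subjects". For the rest, "Samples for the Tier 2 or Tier 3 assessments will be collected if permitted based on the blood or CSF volume threshold" for the child's weight, and subject also to clinical status.

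**Table 4.** Tier 1 includes CSF HS and the row "CSF/Serum Albumin Index (CSF-AI) and IgG index ([CSF/serum IgG ratio] / [CSF-AI". Tier 2 includes:
- a CSF row that starts with HGF, calbindin D and Tau and ends with "albumin, IgG, glutamic acid and glycine";
- serum IgG, in a row with inflammatory and exploratory markers;
- the routine CSF findings, tested locally, in the row "Routine findings (cell counts, glucose, protein".

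SBC-103 in CSF is Tier 3.

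**The primary endpoint (Protocol Section 3.4.1 and synopsis).** The safety assessments include change from baseline in "CSF findings (cell counts, glucose, and protein".

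**When CSF is short (Protocol Section 5.2.1.4).** The first 10 mL is to be collected, with the volume adjustable for age, size and local guidelines. If it is limited, HS comes first, with a pointer to Table 4. No second priority is named.

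**The analysis (SAP Sections 4.1.4, 7.2.2.3 and 7.3.3.1).** CSF findings and CSF-AI are presented in listings only.

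**The concern.** A derived value cannot be more secure than its least secure input. If the protocol requires CSF-AI at every puncture but collects CSF albumin only when volume allows, the requirement cannot always be met, and the site has still done nothing wrong.

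The routine findings raise a separate problem. They are the only CSF component of the primary safety endpoint, yet they compete on equal terms with exploratory markers for whatever CSF remains after HS.

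The allowed volume depends on the child's age and weight, so any gaps would tend to fall in the smaller children rather than at random. There are 11 children, and the SAP drops HS and the other pharmacodynamic data from the report. CSF findings and CSF-AI are therefore the only CSF results that the report will still show.

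**Working it through.** No sample-size or power figure is involved. The check traces each Tier 1 value back to the tier of its inputs, and then looks for other text that would secure the Tier 2 items.

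**Formulas (Protocol Section 5.2.1).**
- CSF-AI = CSF albumin / serum albumin
- IgG index = (CSF IgG / serum IgG) / CSF-AI

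**Tier of each input (Table 4).**

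| Input | Tier | Used in CSF-AI | Used in IgG index |
|---|---|---|---|
| Serum albumin | 1 | yes | yes |
| CSF albumin | 2 | yes | yes |
| CSF IgG | 2 | no | yes |
| Serum IgG | 2 | no | yes |

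**Count.**
- CSF-AI: 1 of 2 inputs is conditional (CSF albumin).
- IgG index: 3 of 4 inputs are conditional (CSF albumin, CSF IgG, serum IgG).
- Routine CSF findings: 3 of 3 components (cell counts, glucose, protein) are conditional.

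**Does other text secure them?**
- Serum albumin is secured twice: it is in Tier 1 chemistry, and Table 4 footnote b and Section 5.2.1.4 require it whenever CSF is taken. The denominator of CSF-AI is protected; the numerator is not.
- Section 5.2.1 asks for all efforts to draw serum albumin and serum IgG with the CSF sample. This helps serum IgG but neither CSF input.
- The schedules of assessments mark CSF albumin, CSF IgG and routine findings at every puncture. They put the same marks on the Tier 3 sample, SBC-103 in CSF, which Section 5.2.1.3 says may be collected if CSF limits have not been exceeded. A schedule mark therefore does not override a tier.
- Section 5.2.1.4 says routine findings will be documented, but the same sentence covers the exploratory CSF biomarkers and refers to Table 4 for detail.

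**Exposure.** SAP Section 4 gives 90 to 110 weeks in Part C before Week 156. Entry is then between 156 − 110 = Week 46 and 156 − 90 = Week 66, so Week 40 falls in Part B. Punctures up to Week 52C are Day 0 and Weeks 12, 24, 28 and 40 (5), plus Day 0C and Weeks 12C, 24C, 40C and 52C (5), about 10 per child. The count varies: a child who enters after Week 52 also has a Week 52 puncture, and a puncture within 4 weeks before Day 0C can stand in for it. This counts opportunities for a gap, not losses.

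**The case against.** The strongest reply is that Table 4 lists albumin and IgG twice for a reason. The Tier 1 row has matrix CSF/Serum, and a mandatory index implies its inputs, so the Tier 2 row would cover albumin and IgG only as stand-alone biomarkers. Section 5.2.1.4 supports that intent, since it adds serum albumin draws so that CSF-AI can be measured at each possible time point. This is a fair reading, but the table does not state it, and a site working row by row could conclude otherwise. It also does nothing for the routine findings, which have no Tier 1 row.

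A second reply is that the order of use for scarce CSF is a matter of judgement. The protocol deliberately puts HS first, and the laboratory manual, which is not available here, may set an aliquot order. HS priority is not in dispute. But the protocol itself ranks a primary-endpoint assessment level with exploratory markers, and it sends the reader to Table 4 for that ranking.

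A third reply is that little depends on this. The SAP plans no inferential analysis, CSF-AI is an exploratory endpoint (Protocol Section 3.4.3), and development was stopped on 11 July 2017, before the SAP of 1 September 2017. This stands, and it limits the point to a low-priority correction.

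**Conclusion.** The tier conflict is in the text. A site following Table 4 could miss a primary-endpoint CSF safety result, CSF-AI or the IgG index without a deviation, and more likely in a smaller child. The number of volume-limited punctures is not given and no assay volumes are stated, so the loss cannot be sized. In the report, the consequence would be blanks in listings for individual children.

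A reader might infer more than the documents support:
- *That IgG is an input to CSF-AI.* It enters only the IgG index. The CSF-AI conflict rests on CSF albumin alone.
- *That Tier 2 tests are optional at the site's choice.* They are conditional on volume and clinical status.
- *That each volume-limited puncture loses every Tier 2 CSF result.* Nothing makes Tier 2 all-or-nothing.
- *That non-random gaps would bias a planned estimate.* The SAP computes none from these data.
- *That the indices belong to the primary endpoint.* They are exploratory. The primary-endpoint consequence comes from the routine findings.

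The conclusion assumes that Table 4 governs collection as written and that no aliquot order in the laboratory manual overrides it.

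**What to change.** - In Table 4, move CSF albumin, CSF IgG, serum IgG and the routine CSF findings to Tier 1. Serum IgG must move too; otherwise the IgG index would still depend on a Tier 2 input.
- In Section 5.2.1.4, state the CSF order in full, because Table 4 has no ranking within a tier: HS first; then routine findings and CSF albumin and IgG; then the remaining exploratory markers (Tier 2); then SBC-103 in CSF (Tier 3). Match the laboratory manual to it.

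The cost is wording in the protocol and manual. The CSF and blood volume limits stay as they are, so no extra CSF is drawn and only its allocation changes. The downside is slightly less CSF for exploratory markers when volume is short, and a small serum IgG volume counted within the blood limit.

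Because development has stopped, retiering serves mainly as a correction if the design is reused. For the present report, the listings could mark CSF results not obtained because of volume. SAP Section 7.2.1.1 promises missing-data handling for each measure, but Section 7.3.3.1 gives none for CSF.

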5.2.1.1 DNA Sample

Where local regulations permit and subject to discretionary approval from each center's IRB/IEC and the consent of the subject (and/or consent of the subject's parent or legal guardian), a whole blood sample will be collected from each subject for DNA extraction.

DNA sequences, including both the protein-coding sequences and the noncoding sequences involved in transcriptional and translational regulation and other biological functions, will be analyzed by the Sponsor for genetic modifications that may contribute to and/or modify the disease phenotype or rate of progression of MPS IIIB. Such DNA sequences, that may be investigated include:

- NAGLU;
- Genes coding for other proteins involved in HS biology that may contribute to and/or modify the disease phenotype of MPS IIIB.

DNA samples will be stored by the Sponsor, or designee, in a secure and controlled environment until analysis, and will be destroyed by the Sponsor after all worldwide obligations have been met, or sooner if required by local regulations.

Refer to the laboratory manual for further details regarding the collection, processing, and storage of these samples.

5.2.1.2 Exploratory Biomarkers

Blood samples for serum isolation will be obtained at the time points specified in the SOA for exploratory analyses to identify and evaluate disease-related biomarkers, where local regulations and blood volume threshold permits. A specific sample for exploratory biomarker analysis is being collected in this study; however, remaining blood and/or urine samples collected in this study may also be used to analyze additional biomarkers of potential clinical interest, if there is sufficient sample and where local regulations permit. These samples will be used to identify baseline disease and dynamic markers that will help the Sponsor to better understand the pathogenesis of MPS IIIB and related comorbidities and response to treatment. Given the rarity of MPS IIIB, the definitive list of analytes remains to be determined.

Collection of samples for exploratory biomarker analysis will be subject to discretionary approval from each center's IRB/IEC and the specific written consent of the subject or the subject's parent or legal guardian. This section of the protocol only applies if approval for collection of these additional samples has been granted by the IRB/IEC and consent is provided by the subject (or the subject's parent or legal guardian).

Samples will be stored by the Sponsor, or designee, in a secure and controlled environment until analysis, and will be destroyed by the Sponsor or designee after all worldwide obligations have been met, or sooner if required by local regulations. Biomarker assays will be performed by a central laboratory or, as appropriate, by academic research laboratories with expertise in the analysis of specific biomarkers.

Refer to the laboratory manual for further details regarding the collection, processing, and storage of these samples.

5.2.1.3 Pharmacokinetic Assessments

As described in Table 5 (Part A), Table 6 (Part B), and Table 7 (Part C) and the SOA, blood samples will be collected to determine SBC-103 serum concentrations using an enzyme-based

PK assay. PK samples collected concurrently with vital sign assessments will be taken prior to collection of blood pressure on the non-infusion arm. PK samples collected at all other time points will be taken at least 5 minutes following deflation of the blood pressure cuff. PK samples should not be taken from the same extremity where the infusion catheter is in place.

CSF samples for determination of SBC-103 concentration in the CSF may also be collected from subjects if CSF volume limitations based on subject's age and weight have not been exceeded.

	Day 0	Week 12	Week 24
Pre-infusion (within 30 minutes)	Х	Х	Х
During Infusion			
30 minutes (±5 minutes)	X	X	Х
90 minutes (±5 minutes) ^a	X	X	Х
120 minutes/End of Infusion ^b (±5 minutes)	X	Х	Х
After Completion of Infusion			
15 minutes (±2 minutes)	X	X	Х
30 minutes (±5 minutes)	X	X	Х
60 minutes (±5 minutes)	X	X	Х
90 minutes (±5 minutes)	X	X	Х
120 minutes (±5 minutes)	X	X	Х
4 hours (±5 minutes)	X	X	X
6 hours (±5 minutes)		X	
8 hours (±15 minutes)	X		X
12 hours (±15 minutes)	X		X
24 hours (±15 minutes) ^a	X		Х

Table 5:PK Sampling in Part A (Initial Therapy)

^aTime points may be omitted, if necessary, to avoid exceeding blood volume limitations.

^bAfter the infusion bag has been emptied, but prior to the flush.

	Week 52	Week 78	Week 104	Week 130	Week 156
Pre-infusion (within 30 minutes)	Х		Х		Х
During Infusion					
30 minutes (±5 minutes)	Х		Х		Х
90 minutes (±5 minutes) ^a	Х	Х	X	Х	Х
120 minutes/End of Infusion ^b (±5 minutes)	Х		X		Х
After Completion of Infusion ^c					
30 minutes (±5 minutes)	Х		Х		Х
120 minutes (±5 minutes)	Х		X		Х
4 hours (±15 minutes)	Х		X		X
6 hours (±15 minutes)	Х		Х		Х

Table 6: PK Sampling in Part B (Therapy at 1 and/or 3 mg/kg)

^aTime point may be omitted, if necessary, to avoid exceeding blood volume limitations.

^bAfter the infusion bag has been emptied, but prior to the flush.

^cTime is relative to the end of the infusion, not the end of the flush.

Note: Subjects may enter Part C at any time point during Part B, therefore not all weeks in Part B may be applicable.

Table 7:	PK Sampling in Part C (Therapy at 5 and/or 10 mg/kg)
----------	--

	Day 0	Wk 12	Wk 24	Wk 52	Wk 78	Wk 104	Wk 130 or End-of-Tx Visit ^a
Pre-infusion (within 30 min.)	Х	Х	Х	X	X	Х	Х
During Infusion							
30 minutes (±5 minutes)	Х	Х	Х	Х	Х	Х	Х
90 minutes (±5 minutes) ^b	X	Х	Х	X	X	Х	Х
120 minutes/End of Infusion ^c (±5 minutes)	X	X	X	X	X	X	Х
After Completion of Infusion ^d							
15 minutes (±2 minutes)	Х	Х	Х	Х	Х	Х	Х
30 minutes (±5 minutes)	Х	Х	Х	X	X	Х	Х
60 minutes (±5 minutes)	Х	Х	Х	Х	Х	Х	Х
90 minutes (±5 minutes)	Х	Х	Х	Х	Х	Х	Х
120 minutes (±5 minutes)	X	Х	Х	Х	Х	Х	Х
4 hours (±5 minutes)	Х	Х	Х	Х	Х	X	X
6 hours (±15 minutes)	X	Х	Х	X	X	Х	X

Key: min. = minutes; Tx = treatment; Wk = Week

^aWeek 130 in Part C or the subject's end-of-therapy visit (ie, Week 156 of the study or early termination visit) ^bTime point may be omitted, if necessary, to avoid exceeding blood volume limitations.

^cAfter the infusion bag has been emptied, but prior to the flush. ^dTime is relative to the end of the infusion, not the end of the flush.
5.2.1.4 Lumbar Puncture (Cerebrospinal Fluid)

Lumbar punctures will be performed for the collection of CSF at the time points specified in the SOA. The coagulation laboratory panel should be collected within 48 hours prior to performing the lumbar puncture, and the results should be available prior to sedating/anesthetizing the subject or performing the lumbar puncture. At Day 0, the lumbar puncture (including the initiation of sedation/anesthesia) shall not commence until the site receives the coagulation results, confirms that a subject continues to meet eligibility, and provides such documentation to the Sponsor for review and agreement. For all other lumbar punctures during the study, the procedure (including the initiation of sedation/anesthesia) will not commence until the site receives these results and confirms that it is safe for the subject to receive anesthesia/sedation and the lumbar puncture. This documentation should be filed as part of the subject's file and does not need to be reviewed by the Sponsor before the procedure. To facilitate this process, all coagulation panels (as of 23 March 2015) will be drawn and analyzed locally rather than sent to the central laboratory for analysis.

The lumbar puncture may be performed under general anesthesia, if clinically appropriate, or under light sedation and will be performed as per local practices by a qualified professional in accordance with local institutional procedures. The first 10 mL of CSF will be collected and mixed gently to avoid gradient effects. The actual volume may be adjusted based on subject age or size and local institutional guidelines. If CSF volume is limited, the analysis of CSF HS (total and NRE) should be prioritized as noted in Table 4.

Routine CSF findings will also be documented (eg, cell counts, glucose, and protein levels), and MPS IIIB substrate (HS) and other exploratory CSF biomarkers will be analyzed (see Table 4 for details).

Per the SOA, collection of serum chemistry will not always coincide with the collection of CSF. In order to measure the CSF-AI at each possible time point, a serum albumin sample should be collected at time points where a serum chemistry sample is not being collected at the same day as the CSF sample. After the lumbar puncture is completed, the subject should be observed as per institution standard practice. Vital signs should be obtained prior to discharge. Any AEs or changes to concomitant medications should also be assessed.

5.2.2 Facial Dysmorphology Novel Analysis

Facial photographs will be obtained for Facial Dysmorphology Novel Analysis (FDNA) at the time points specified in the SOA. This technology enables automatic detection and evaluation of subtle cranio-facial dysmorphology associated with multiple rare diseases, by processing and analyzing standard 2-dimensional (2D) facial photos. The FDNA system uses proprietary computer algorithms to recognize and describe subtle craniofacial malformations (out of a list of clinically relevant anatomical facial features) in mathematical terms. A ranked score, representing the probability of the genetic syndrome, is produced based on analysis of the severity of the facial alterations relative to variations in a normal population, as well as recognition of the face "gestalt" associated with certain rare diseases. FDNA offers potential as a tool for screening large populations for MPS IIIB, which may enable wider and earlier diagnosis of MPS IIIB patients, as well as providing a means for monitoring progression of disease in patients diagnosed with MPS IIIB. This study will evaluate FDNA technology as a means to evaluate both clinical characteristics and course of disease progression in MPS IIIB. FDNA assessment will be optional based on subject/parent consent to participate. A subject/caregiver may refuse this assessment and still participate in this study. Once a

subject/caregiver consents to this assessment, all attempts should be made to collect data at each study time point.

